6.2.4 Patient Global Impression of Change (PGI-C)

Global improvement will be rated by the patient using the PGI-C. Whenever feasible, assessments should be made by the same assessor in an individual patient. The assessments will be carried out at the time points noted in the schedule of assessments ([Table 4](#)).

6.2.5 Clinical Global Impression (CGI-C)

Global improvement will also be rated by the investigator or designee separately using the CGI-C. Whenever feasible, assessments should be made by the same assessor in an individual patient. The assessments will be carried out at the time points noted in the schedule of assessments ([Table 4](#)).

6.2.6 Mini-Mental State Examination (MMSE)

The MMSE is a scale for eligibility. It comprises a 30-point questionnaire that is used extensively in clinical and research settings to measure cognitive impairment. It is used to estimate the severity and progression of cognitive impairment and to follow the course of cognitive changes in an individual over time; thus, making it an effective way to document an individual’s response to treatment. The assessments will be carried out at Screening.

6.3 Pharmacokinetics Assessments

The PK measure will be the determination of plasma concentration of pridopidine and its metabolite TV-45065 using a validated liquid chromatography–mass spectrometry method.

Details on PK sample collection are detailed in [Section 6.9](#).

6.4 Pharmacogenetic and Plasma Biomarker Assessments

Details on pharmacogenetic and plasma biomarker sample collection are detailed in [Section 6.9](#).

6.4.1 Pharmacogenetic Assessments

Pharmacogenetic assessments may include the analysis of DNA variations (e.g., known polymorphism in the σ_1R gene and the catechol-O-methyltransferase [COMT] gene) with a potential relationship with clinical responses to study drug (e.g., efficacy, PK, tolerability, safety features or disease susceptibility, and severity features). The final list of genes that might be investigated will be selected at a later stage before the analysis to allow updating with new scientific information. Genetic analysis could also include sequencing of the whole genome if required. The genetic sample analysis will be performed if and when required. Since new techniques continue to be developed, the method and laboratory that will be used for the genetic analysis cannot be defined at present. The bioanalytical laboratory will be identified at a later stage.

6.4.2 Plasma Biomarker Assessment

The following biomarker candidate assessments will be evaluated: neurofilament light chain protein (NFL), α -synuclein, and DJ-1. Other blood biomarkers may be evaluated for future exploratory purposes upon new scientific knowledge.

6.5 Safety Assessments

Safety assessments include AEs, concomitant medications, laboratory tests (clinical chemistry, haematology, and urinalysis), C-SSRS, 12-lead ECG, QUIP-RS, vital signs (including assessment of orthostatic hypotension), and physical and neurological examination. The assessments will be carried out at the time points noted in the schedule of assessments (Table 4). Every effort should be made to ensure that, for a given safety assessment, all measurements are performed by the same rater for each individual patient for all visits.

6.5.1 Adverse Events

6.5.1.1 Definitions of Adverse Events

The investigator is responsible for reporting all AEs that are observed or reported during the study, from the signing of the IRB-approved ICF to the last study visit or until satisfactory resolution, regardless of their relationship to study treatment or their clinical significance.

An AE is defined as any untoward medical occurrence in a patient enrolled into this study regardless of its causal relationship to study treatment. Patients will be instructed to contact the investigator at any time after randomization if any symptoms develop.

A treatment-emergent AE (TEAE) is defined as any event not present before exposure to study treatment or any event already present that worsens in either intensity or frequency after exposure to study treatment.

6.5.1.2 Serious Adverse Events

An SAE is defined as any event that:

- results in death
- is immediately life-threatening
- requires inpatient hospitalization or prolongation of existing hospitalization
- results in persistent or significant disability/incapacity
- is a congenital anomaly/birth defect

Important medical events that may not result in death, be life-threatening, or require hospitalization may be considered SAEs when, based upon appropriate medical judgment, they may jeopardize the patient or may require medical or surgical intervention to prevent one of the outcomes listed in this definition. Examples of such medical events include allergic bronchospasm requiring intensive treatment in an emergency room or at home, blood dyscrasias or convulsions that do not result in inpatient hospitalization, or the development of drug dependency or drug abuse.

6.5.1.3 Eliciting and Documenting Adverse Events

Adverse events will be assessed beginning at enrollment (date of signed informed consent) and up to visit of the safety follow-up period (Visit 8).

Serious AEs that occur more than 30 days after the reporting period need not be reported unless the investigator considers them related to study treatment.

At every study visit, patients will be asked a standard nonleading question to elicit any medically related changes in their well-being. Patients will also be asked if they have been hospitalized, had any accidents, used any new medications, or changed concomitant medication regimens (both prescription and OTC medications).

In addition to patient observations, any abnormal laboratory test results (haematology, clinical chemistry, or urinalysis) or other safety assessments (e.g., ECGs, radiological scans, vital sign measurements), including those that worsen from Visit 2, felt to be clinically significant in the medical and scientific judgment of the investigator are to be recorded as AEs or SAEs. In addition, AEs identified from review of other documents (e.g., patient diaries) that are relevant to patient safety will be documented on the AE page in the eCRF.

6.5.1.4 Reporting Adverse Events

All AEs reported or observed during the study will be recorded on the AE page in the eCRF. Information to be collected includes the following:

- drug treatment
- dose
- event term
- time of onset
- investigator-specified assessment of severity and relationship to study treatment
- time of resolution of the event
- seriousness
- any required treatment or evaluations
- outcome

Adverse events resulting from concurrent illnesses, reactions to concurrent illnesses, reactions to concurrent medications, or progression of disease states must also be reported. All AEs will be followed to appropriate resolution. The Medical Dictionary for Regulatory Activities (MedDRA) will be used to code all AEs.

Any medical condition that is present at the time that the patient is screened but does not deteriorate should not be reported as an AE. However, if it deteriorates at any time during the study, it should be recorded as an AE. Pharmacodynamic symptoms of the treatment are not considered as an AE. Overdoses without signs or symptoms do not need to be recorded as AEs; in case of any AEs associated with the overdose, these should be reported on relevant AE/SAE sections in the eCRF ([Section 5.5](#)).

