6.5.1.8 Assessment of Causality

Every effort will be made by the Investigator to assess the relationship of the AE, if any, to the study treatment. Investigators should use their knowledge of the patient, the circumstances surrounding the event, and an evaluation of any potential alternative causes to determine whether or not an AE is considered to be related to the study treatment. Causality should be assessed using the categories presented below:

Related: Adverse event judged by the Investigator as having a reasonable suspected causal relationship to the investigational medicinal product

Unrelated: Adverse event judged by the Investigator as NOT having a reasonable suspected causal relationship to the investigational medicinal product

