6.5.1.9 Exceptions

In this protocol, symptoms and signs related to PD will not be considered as AEs or captured on the eCRF, however, unexpected worsening of PD should be reported as an AE. The following hospitalization scenarios will not be considered AEs:

- Hospitalization for a preexisting condition, provided that the following criteria are met:
 - The hospitalization was planned prior to the study or was scheduled during the study when elective surgery became necessary because of the expected normal progression of the disease or
 - The patient has not experienced an AE

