The patient must be in a supine position and resting for at least 5 minutes prior to each ECG measurement. Where applicable, ECG measurements should be taken prior to vital sign measurements and blood being drawn for clinical laboratory or PK evaluations. A qualified physician at the central ECG vendor will be responsible for interpreting the ECG and send results within 24 hours. However, every ECG should be reviewed immediately at site for the purpose of determining any gross abnormality (like new atrial fibrillation or QTcF prolongation) that might affect patient safety and not allow dosing. If the local ECG reading results at the site match any of the discontinuation criteria (see [Section 4.2.1](#)), the patient should stop taking study treatment until the central ECG reader's report is received. If the central reader does not report a QTcF interval that would lead to discontinuation according to the above, then the patient should restart study treatment. Any ECG finding that is judged by the investigator or the physician from the central ECG vendor as a clinically significant change (worsening) compared with a Visit 2 value will be considered an AE, recorded on the source documentation and transcribed onto the eCRF and monitored as described in [Section 6.5.1.4](#).

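### Protocol 6.5.1.4 excludes undefined pharmacodynamic symptoms from adverse events, which contradicts the definition in 6.5.1.1 and can shrink the active-placebo difference in recorded TEAE rates

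*Protocol*

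**What the plan says.** Protocol 6.5.1.1 gives the definition: "An AE is defined as any untoward medical occurrence in a patient enrolled into this study regardless of its causal relationship to study treatment". The investigator must report all AEs "regardless of their relationship to study treatment or their clinical significance". In the same section a treatment-emergent AE (TEAE) is "any event not present before exposure to study treatment or any event already present that worsens in either intensity or frequency" after exposure, with no exemption for drug action.

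Protocol 6.5.1.4 then says: "Pharmacodynamic symptoms of the treatment are not considered as an AE". It gives no definition, list, severity limit or seriousness limit, and does not mention treatment arm.

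Four other places bear on this:

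- 6.5.1.8 has a Related category: "Adverse event judged by the Investigator as having a reasonable suspected causal relationship to the investigational medicinal product".
- 6.5.1.9, the section set aside for exceptions, says that "symptoms and signs related to PD will not be considered as AEs or captured on the eCRF", keeps unexpected worsening of PD reportable, and exempts some hospitalizations. It does not mention pharmacodynamic symptoms.
- 6.5.1.3 says that abnormal laboratory results and other safety assessments "felt to be clinically significant in the medical and scientific judgment of the investigator are to be recorded as AEs or SAEs".
- 6.5.2 says that a clinically significant ECG worsening "will be considered an AE, recorded on the source documentation and transcribed onto the eCRF".

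The SAP (15.3) builds its TEAE tables from recorded AEs by treatment group.

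**The concern.** A definition that ignores cause cannot stand beside a rule that removes events because of their cause. An investigator who believes that a patient's new symptom comes from the drug's action is told by 6.5.1.1 to record it and by 6.5.1.4 that it is not an AE.

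If the second instruction is followed, the symptom never reaches the AE page. It is then missing from the TEAE tables and possibly from the count of patients who stop because of AEs. Nothing in the SAP can bring it back, because its analyses start from what was recorded.

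The category could be wide. Protocol 1.2.1.2 describes binding at adrenergic, dopamine, serotonin, histamine and muscarinic sites, so many untoward symptoms could be called pharmacodynamic. Capture also matters because the 150 mg BID arm is above 112.5 mg BID, which Protocol 1.2.1.1 names as the highest dose tested in humans.

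**Working it through.** The plan gives no figure on this point, so there is none to reproduce. The check sets the sections against each other and then illustrates the direction of the effect.

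**1. Can the sentence be read so that it agrees with 6.5.1.1?**

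- *It means only the intended benefit.* Reduced dyskinesia is not untoward, so it was never an AE under 6.5.1.1. On this reading the sentence does nothing, and it does not say that this is its scope.
- *It means the effects of levodopa.* The wording is the treatment, not study treatment, so this is possible. But 6.5.1.4 itself requires reactions to concurrent medications to be reported, so this reading creates a second contradiction.
- *It means untoward effects of pridopidine.* This contradicts 6.5.1.1 directly and leaves the Related category in 6.5.1.8 with little to hold.

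No reading both gives the sentence a function and removes the conflict.

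**2. Do neighbouring exclusions carry a limit that this one lacks?** Yes. In 6.5.1.4 a pre-existing condition becomes an AE if it deteriorates, and an overdose with signs or symptoms leads to AE reporting. In 6.5.1.9 unexpected worsening of PD is reported. The pharmacodynamic exclusion has no such limit.

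**3. What is still captured?**

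- clinically significant laboratory, vital-sign and ECG findings (6.5.1.3, 6.5.2);
- clinically significant decreases in creatinine clearance (6.8);
- discontinuations under the QTcF rules, as AEs of special interest (6.5.1.6).

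The remaining gap is mainly symptoms with no objective finding.

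**4. Direction of the effect.** All rates here are assumptions and none comes from the documents. Let p0 and p1 be the true rates of such symptoms on placebo and active drug, and s the share judged pharmacodynamic and not recorded.

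- Case (a): blinded assessors drop the same share in every arm. Recorded rates are p0(1 − s) and p1(1 − s).
- Case (b): only the drug-caused excess is dropped. Recorded rates are p0 and p0 + (p1 − p0)(1 − s).

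In both cases the recorded difference is (p1 − p0)(1 − s).

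| True placebo / active | s | (a) placebo / active | (b) placebo / active | Recorded difference |
|---|---|---|---|---|
| 10% / 30% | 25% | 7.5% / 22.5% | 10% / 25% | 15 points |
| 10% / 30% | 50% | 5% / 15% | 10% / 20% | 10 points |
| 10% / 30% | 100% | 0% / 0% | 10% / 10% | 0 points |
| 5% / 20% | 25% | 3.75% / 15% | 5% / 16.25% | 11.25 points |
| 5% / 20% | 50% | 2.5% / 10% | 5% / 12.5% | 7.5 points |
| 5% / 20% | 100% | 0% / 0% | 5% / 5% | 0 points |

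The true differences are 20 and 15 points. The absolute difference shrinks equally in both cases, but the ratio does not. With 10% and 30% and s = 50%, the ratio stays at 15/5 = 3 in case (a) and falls from 3 to 20/10 = 2 in case (b).

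**The case against.** The strongest reply is that the sentence is loose drafting and that the rest of the protocol contains it. An AE must be untoward, relationship to study treatment is collected for each AE, and a Related category exists, so the authors plainly expected drug-caused events to be recorded. That is a fair guess at intent. It does not tell a site what to do with an untoward symptom that it attributes to the drug, and the sentence as written says not to count it.

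The second reply is that other data act as a backstop. This stands in part. Beyond the findings in step 3 of the working, QTcF, orthostatic blood pressure, C-SSRS and QUIP-RS are collected separately (Protocol 7.3), and reasons for withdrawal are recorded (4.2.2). These cover measured findings and two specific domains, not symptoms in general. The SAP also puts physical examination, C-SSRS and QUIP-RS in listings only (15.7, 15.8).

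Some stronger readings are tempting, and the documents do not support them:

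- *The exclusion affects the active arms only, or is differential by construction.* The sentence has no arm restriction, and the physician who assesses AEs is among those blinded (Protocol 5.8). Look-alike symptoms on placebo can be dropped too. If the same share is dropped in every arm, the absolute difference shrinks but the ratio is unchanged.
- *Formal safety-board review was weakened.* SAP 9.3 says that no formal DSMB meeting was held. Only the real-time review of SAEs planned in Protocol 6.6 could be touched. Even there, 6.5.1.2 defines an SAE as any event with the listed outcomes, although 6.5.1.5 words the reporting duty in terms of AEs that meet those criteria.
- *One lost event is worth about 10 percentage points.* SAP 9.3 says only that the trial stopped before 30 subjects were enrolled. The numbers per arm are not given.

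**Conclusion.** The point holds. Section 6.5.1.4 is wrong as written: it contradicts the definition and reporting duty in 6.5.1.1, fits badly with 6.5.1.3, 6.5.1.8 and 6.5.1.9, and is not corrected in the SAP.

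If blinded assessors follow it, untoward symptoms can go unrecorded in any arm. Because truly drug-caused symptoms occur only on pridopidine, the expected result is under-recording of AEs and an absolute active-placebo difference in TEAE rates reduced by the factor (1 − s). This rests on the assumption that s is the same in every arm or falls only on the drug-caused excess.

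The size is unknown. The documents give neither s nor the symptom rates, and do not show whether any site applied the sentence. At the planned 45 patients per arm, one patient is 1/45 = 2.2 percentage points. That is the weight of a single unrecorded case, not an estimate of how many there were.

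**What to change.** Reconcile Protocol 6.5.1.1, 6.5.1.3, 6.5.1.4, 6.5.1.8 and 6.5.1.9 in one of two ways:

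- delete the sentence; or
- limit it to the intended therapeutic effect, and state that any untoward occurrence is an AE, and is assessed against the SAE criteria, whatever its mechanism.

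Editing the text does not recover symptoms that were never written down. SAP section 2 places its finalization before database lock and unblinding. So, before lock, ask each site whether it withheld any symptom under this sentence, add those that can be documented, and state the answer in the study report, including if it is none.

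The cost is one sentence in the protocol and eCRF guidance, a short site query, and slightly more AEs recorded.

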6.5.1.5 Reporting Serious Adverse Events, Pregnancy, and Overdose

Any AEs reported or observed during the study from informed consent that meets SAE criteria ([Section 6.5.1.2](#)) must be reported to the [REDACTED] immediately (i.e., within 24 hours) after the time site personnel first learn about the event. Any pregnancy that occurs during study participation must be reported using the same procedures as an SAE, i.e., within 24 hours of first knowledge using a pregnancy report form. The investigator should also be notified of pregnancy occurring during the study but confirmed after completion of the study. In the event that a patient is found to be pregnant after inclusion in the study, any pregnancy will be followed to term, and after delivery, the status of mother and child will be reported to the sponsor after delivery. Full details will be recorded on the withdrawal page of the eCRF.

Any overdose, with or without associated AEs, must be promptly reported to the Sponsor [REDACTED] in an expedited manner using the SAE Report Form, and following the procedure described in this section and from [REDACTED]. The patient may be hospitalized for observation and appropriate supportive treatment administered. Any concerning overdose (i.e., with an associated AEs or any lab abnormalities) will be reported

Prilenia Therapeutics

Protocol: PL101-LID201 Protocol Amendment 1/v2.0

Pridopidine

19 Nov 2019

via [REDACTED]. Any AE/SAEs or any lab abnormalities considered related to the overdose should be reported as appropriate.

The determination of an overdose will be left to the discretion of the investigator, based on the quantity of overdose, emergence of any clinical signs and symptoms suggestive of toxic administration, as well as his/her own clinical judgment as it applies to each individual case.

Overdoses without signs or symptoms do not need to be recorded as AEs; in case of any AEs associated with the overdose, these should be reported on relevant AE/SAE sections in the eCRF.

The following contact information is to be used for SAE reporting:

[REDACTED]
[REDACTED]
[REDACTED]

Investigators must report SAEs and follow-up information to their responsible IRB or independent ethics committee (IEC) as applicable per institutional policy.

The sponsor or designee will provide regulatory authorities, IRBs, IECs, and principal investigators with clinical safety updates/reports according to local requirements.

6.5.1.6 Suspected Unexpected Serious Adverse Reactions and Nonserious Adverse Events of Special Interest

The sponsor will promptly evaluate all SUSARs against cumulative product experience to identify and expeditiously communicate possible new safety findings to investigators, IRBs/IECs, and applicable health authorities based on applicable legislation.

To determine reporting requirements for single AE cases, the sponsor will assess the expectedness of these events using the study treatment investigator's brochure.

Prilenia Therapeutics will compare the severity of each SUSAR and the cumulative event frequency reported for the study with the severity and frequency reported in the applicable reference document.

Reporting requirements will also be based on the investigator's assessment of causality and seriousness, with allowance for upgrading by the sponsor as needed. All AEs will be evaluated with equal interest.

Events of discontinuation due to meeting the QTcF stopping rules (defined in [Section 4.2.1](#)) will be considered AEs of special interest.

6.5.1.7 Assessment of Severity

The severity, or intensity, of an AE refers to the extent to which an AE affects the patient's daily activities. The intensity of the AE will be rated as mild, moderate, or severe using the following criteria:

Mild: These events require minimal or no treatment and do not interfere with the patient's daily activities.

Moderate: These events result in a low level of inconvenience or concern with the therapeutic measures. Moderate events may cause some interference with normal functioning.

An AE that is sufficiently discomforting to interfere with normal activities.

Severe: These events interrupt a patient's usual daily activity and may require systemic drug therapy or other treatment. Severe events are usually incapacitating.

Changes in the severity of an AE should be documented to allow an assessment of the duration of the event at each level of intensity to be performed. Adverse events characterized as intermittent do not require documentation of onset and duration of each episode.

6.5.1.8 Assessment of Causality

Every effort will be made by the Investigator to assess the relationship of the AE, if any, to the study treatment. Investigators should use their knowledge of the patient, the circumstances surrounding the event, and an evaluation of any potential alternative causes to determine whether or not an AE is considered to be related to the study treatment. Causality should be assessed using the categories presented below:

Related: Adverse event judged by the Investigator as having a reasonable suspected causal relationship to the investigational medicinal product

Unrelated: Adverse event judged by the Investigator as NOT having a reasonable suspected causal relationship to the investigational medicinal product

